LA	Local Anaesthesia
LMV	Läkemedelsverket, Swedish medical products agency
MCID	Minimal clinically important difference
NRS	Numeric Rating Scale
PACU	Post Anesthesia Care Unit
PCS	Patient-controlled sedation
QoR-15 swe	Quality of Recovery-15 swedish
RCT	Randomized Controlled Trial
SFAI	Swedish Society for Anaesthesia and Intensive Care
SPOR	Swedish Perioperative Register
SVP	Subcutaneous Venous Port
TIVAD	Totally Implantable Venous Access Device

2 Introduction

Cancer requiring chemotherapy is common. Approximately 70.000 patients are diagnosed with cancer in Sweden every year often leaving patients in need of intravenous chemotherapy.

Subcutaneous venous ports (SVP) are commonly used in cancer patients to facilitate intravenous administration of chemotherapy, blood sampling and administration of other medications.

The implantation of SVPs is a minor surgical procedure and one of Sweden's most common according to the Swedish Perioperative Register (SPOR). SVP implantation is usually performed in a day case surgery setting and the patient released home within a few hours after the procedure.

Conventional outcomes measured after surgery have focused on morbidity, mortality, pain scores, analgesic consumption, etc. However, these measures represent only one aspect of a patient's recovery [1].

'Quality of Recovery' scores are patient-reported outcome measures (PROM) evaluating recovery after surgery and anaesthesia reflecting the patient's ability to resume normal activities and are an important indicator of a successful perioperative experience [1].

The Quality of Recovery-15 (QoR-15) is a psychometrically evaluated instrument with high reliability and validity, high responsiveness and good return rates in the postoperative setting [2]. It provides a meaningful overall evaluation of a patient's recovery after surgery [3]. Fifteen questions assess five domains of patient-reported health status: pain, physical comfort, physical independence, psychological support and emotional state. The 11-point numerical rating scale leads to a minimum score of 0 (very poor recovery) and a maximum score of 150 (excellent recovery). QoR-15 scores negatively correlate with duration of surgery and analgesic usage. Its minimal clinically important difference (MCID) describes the smallest change in score that constitutes a meaningful change in health status and is recommended to be a value of six [4]. The Swedish version of QoR-15swe has recently been validated [5].

A common perception of postoperative recovery in cancer patients undergoing SVP implantation is that recovery is good. We hypothesize that postoperative QoR-15 score is unaffected among patients undergoing SVP implantation, randomized to PCS. To our knowledge no study has investigated postoperative recovery after SVP implantation in general and the influence of PCS in particular.

The aim of this pre-planned sub-study of the PACSPI trial (PACSPI-2, EUDRACT NUMBER 2021-003821-31) is to assess postoperative recovery, measured as QoR-15 among patients randomized to patient-controlled sedation (PCS) with alfentanil and propofol as adjunct to local anaesthesia (LA) during SVP implantation or standard care with LA. Patients participating in the study are interviewed with QoR-15 at three different time points; preoperatively (baseline), postoperatively at the post anaesthesia care unit (PACU, before discharge) and 24 hours postoperatively (by telephone).

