2.1 Purpose of the analyses

The analyses will assess recovery scores measured by QoR-15. The analyses will assess if there are differences in QoR-15 scores due to PCS intervention.

3 Study Objectives and Endpoints

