3.1 Study Objectives

This study measures postoperative outcome of cancer patients undergoing SVP implantation evaluated with QoR-15 and the influence of PCS on postoperative recovery. The study was pre-planned within 'Patient-controlled sedation in subcutaneous port implantation- a randomized controlled trial' (PACSPI-2, EUDRACT NUMBER 2021-003821-31) which assesses the efficacy of patient-controlled sedation (PCS) with alfentanil and propofol as adjunct to local anaesthesia during SVP implantation. Patients participating in the study are interviewed with QoR-15 at three different time points; preoperatively (baseline), postoperative in PACU (before discharge) and 24 hours postoperatively (by telephone). Assessment of QoR-15 scores between groups and time points are the study objectives in these analyses.

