3.2 Endpoints

Primary endpoint:

The primary endpoint is assessment of change in total QoR-15 score between groups at the time points.

Secondary endpoints:

Secondary endpoint is assessment of difference for each QoR dimension and for each of Parts A and B within and between groups.

Secondary endpoint is assessment of analgesic consumption and patient-reported postoperative pain perception between groups.

4 Study Methods

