Considering a minimal clinically important difference (MCID) of 6 that has been suggested to constitute a meaningful change in health status with a standard deviation of 19 a total number of 314 patients is needed to detect this change with 80% power, 2-sided, at a significance level of 5%.

6 General Considerations

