6.6 Demographic and Baseline Variables

Gender, age, American Society of Anesthesiologists (ASA)-class, BMI, cancer type, treatment strategy, preoperative analgesia, procedural time, sedation score at timepoints T1-4 (OAAS), sedation volym, alfentanil (mg) delivered, propofol (mg) delivered will be reported for demographic and interventional data.

7 Statistical Analyses

The analysis will be produced on intention to treat population.

Data will be summarised by treatment group. Summary statistics of demographic and baseline variables will be reported. All continuous variables will be summarised using the following descriptive statistics: n (non-missing sample size), median, interquartile range. The frequency and percentages (based on the non-missing sample size) of observed levels will be reported for all categorical measures. Categorical data will be analysed with Chi2 test, continuous data will be analysed with Mann-Whitney U test.

Repeated measurement of analysis of variance is used for the analysis of treatment effect of PCS on QoR-15 scores. This model takes the inter- and intra-individual variation into account and provides flexibility in handling missing data which will be reported. Fixed factors include treatment group, time and treatment-by time-interaction. Confidence intervals will be reported and adjustment for planned comparison conducted. Testing will be two-sided with a 5% significance level.

Demographic and baseline data will be listed by treatment group in a table.

Primary endpoint will be displayed in a figure.

Secondary endpoints will be displayed in a figure.

8 Reporting Conventions

P-values ≥ 0.01 will be reported to two decimal places, p-values ≥ 0.001 will be reported to three decimal places; p-values less than 0.001 will be reported as “ <0.001 ”. The median and any other statistics other than quantiles, will be reported to one decimal place greater than the original data.

9 Technical Details

Analyses will be carried out with the study statistician. Analyses will be carried out in SPSS, IBM

References

<http://dx.doi.org/10.1093/bja/aev413>.
<http://dx.doi.org/10.1097/ALN.0b013e318289b84b>.

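### The Protocol hypothesises that QoR-15 is unaffected by PCS but plans only a test for a difference, with no rule for reading the confidence interval against the MCID of 6

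*Protocol*

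**What the plan says.** The only hypothesis about QoR-15 in either document is in the Protocol, section 2 (Introduction): "We hypothesize that postoperative QoR-15 score is unaffected among patients undergoing SVP implantation, randomized to PCS".

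The later Protocol sections are framed as a search for a difference:

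- Section 2.1 (Purpose of the analyses): "The analyses will assess if there are differences in QoR-15 scores due to PCS intervention".
- Section 3.1 (Study Objectives): "Assessment of QoR-15 scores between groups and time points are the study objectives in these analyses".
- Section 3.2 (Endpoints) gives the primary endpoint as "assessment of change in total QoR-15 score between groups at the time points".
- Section 5 (Sample Size) takes the MCID of 6 as the effect to detect: "a total number of 314 patients is needed to detect this change with 80% power, 2-sided, at a significance level of 5" per cent.
- Section 7 (Statistical Analyses) plans a repeated-measures model with treatment, time and their interaction. It adds "Confidence intervals will be reported and adjustment for planned comparison conducted" and "Testing will be two-sided with a 5% significance level".

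Section 2 also introduces 6 points as the smallest change that matters to patients. Section 7 does not use that figure.

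The SAP covers the parent pain trial. It lists QoR-15 among the secondary endpoints (section 4.3), describes it by n, median and interquartile range (section 5.6), and leaves its results to a separate manuscript (section 18). It gives no QoR-15 hypothesis, margin or reading rule.

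**The concern.** A test of the null hypothesis of no difference can reject that hypothesis but cannot establish it. A claim that recovery is unaffected needs the data to exclude differences large enough to matter, which means comparing the interval with a stated margin. The Protocol has both ingredients, a reported interval and an MCID, but does not connect them.

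What is at stake is the conclusion on the primary endpoint, not the estimate. If the test is non-significant, the text allows the result to be described as agreeing with the hypothesis even when the interval includes a difference that the Protocol itself calls meaningful. A reading rule chosen after the results are known would be discretionary.

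**Working it through.** **Inputs.** Difference of 6, SD 19, 80% power, two-sided 5% (Protocol section 5); 340 patients, 1:1 (sections 4.1 and 5); less than 10% of data missing (section 6.3). Taking the full 10% as lost patients gives 340 × 0.9 = 306, or 153 per arm, which is a worst case. With no loss there are 170 per arm.

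**The plan's own figure.** The two-sample formula for detecting a difference gives, per arm, 2 × (19 × (1.960 + 0.842) / 6)² = 157.4. The total is 314.8, which truncates to the stated 314 (316 if each arm is rounded up). The figure reproduces, and it is a size for detecting a difference.

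**Precision of one unadjusted two-group comparison.** SE = 19 × √(2/n). The half-width is t × SE, with t = 1.968 at 306 patients and 1.967 at 340.

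| | 306 evaluable | 340 evaluable |
|---|---|---|
| SE | 2.172 | 2.061 |
| 95% half-width, h (also the largest non-significant difference) | 4.27 | 4.05 |
| Interval limit at that difference, 2h | 8.5 | 8.1 |
| Interval excludes 6 only if the observed difference is below 6 − h | 1.73 | 1.95 |

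An observed difference from about 1.7 to 4.3 (306 patients) or 1.9 to 4.1 (340 patients) is therefore non-significant with an interval that still includes 6.

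**How often this matters.**

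- True difference 6: by the noncentral t distribution, the chance of a non-significant result is 0.214 at 306 and 0.173 at 340.
- True difference 0 (normal approximation): the chance that the 95% interval lies wholly within ±6 is 2Φ(6/SE − 1.960) − 1.
  - At 306: 6/2.172 = 2.762, giving 0.577.
  - At 340: 6/2.061 = 2.911, giving 0.659.
  - Non-significant without excluding 6: 0.950 − 0.577 = 0.373 and 0.950 − 0.659 = 0.291.

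**With an adjustment.** Section 7 plans one but does not name it. If it were Bonferroni over the two post-baseline time points (an assumption), each interval would be at 97.5%, with z = 2.241.

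- The half-width becomes about 4.9 at 306 and 4.6 at 340.
- With no true difference, the chance of lying within ±6 is 2Φ(2.762 − 2.241) − 1 = 0.397 and 2Φ(2.911 − 2.241) − 1 = 0.497.
- The inconclusive share per comparison is 0.975 − 0.397 = 0.578 and 0.975 − 0.497 = 0.478.

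**If equivalence were the aim.** Suppose a margin of ±6 (the documents set none), one time point and no true difference. A 90% interval (z = 1.645) gives power 2Φ(2.762 − 1.645) − 1 = 0.736 at 306 and 2Φ(2.911 − 1.645) − 1 = 0.795 at 340. A 95% interval gives 0.577 and 0.659, as above.

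**The case against.** The strongest reply is that the no-effect wording is one sentence of background. The purpose, objectives, endpoint, sample size and analysis sections are all consistent with a difference trial. Investigators may expect little effect and still run an ordinary two-sided test, and many difference trials prespecify no reading rule. The Protocol promises intervals and states the MCID, so a reader could make the comparison unaided. The two-sided 5% level also implies a 95% interval before adjustment, so the interval level is not really missing.

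Much of this stands, and it limits the weight of the point. A reader might infer that the sponsor intends to treat p above 0.05 as proof of no effect, or that this is an equivalence trial with the wrong test and the wrong size. The documents support neither. They never call the study equivalence or non-inferiority, never say that a non-significant result confirms anything, and size the trial correctly for the difference test they describe.

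The reply does not remove the mismatch. The sentence is the only hypothesis stated for QoR-15, and it follows directly on the remark that recovery is commonly perceived as good, so it reads as the expected finding. Having the interval and the MCID available is not the same as committing in advance to how they will be compared.

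It is also fair to say that the figures come from a single two-group comparison, not from the planned repeated-measures model, whose precision may differ. An adjustment for several comparisons would widen the intervals.

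**Conclusion.** The concern holds as a mismatch between the stated hypothesis and what the planned test can show. It is not an error in the test, the estimate or the sample size. A non-significant result alone cannot support the claim that QoR-15 is unaffected, and the plan gives no other rule that could.

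For one unadjusted comparison, the chance of a non-significant result that fails to exclude 6 is about 37% (306 evaluable) to 29% (340) when there is no true difference. When the true difference is 6, about 21% to 17% of trials would be non-significant. These figures assume that SD 19 applies to the quantity compared, that the arms are equal, and that 10% loss is the worst case.

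The priority is low to moderate: the repair is cheap and governs what may be said about the primary endpoint, but the source is a single sentence.

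**What to change.** **Preferred.** Reword the hypothesis in Protocol section 2, for example: *We will assess whether the postoperative QoR-15 score differs between patients randomized to PCS and to LA alone.* Then add to section 7:

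> A p-value above 0.05 will not be taken as evidence of no effect. For each post-baseline time point (PACU and 24 h), the confidence interval for the between-group difference in change in total QoR-15, at the level that matches the planned adjustment for comparisons, will be read against the MCID of 6. An interval wholly within ±6 will be reported as excluding a clinically important difference at that time point, whether or not it excludes zero. A non-significant result whose interval reaches 6 or more in either direction will be reported as inconclusive. A general statement that QoR-15 is unaffected will be made only if the intervals at both time points lie within ±6 and include zero.

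**Alternative.** Keep the no-effect hypothesis as equivalence. Prespecify a margin no larger than 6, the interval level and the time point, and state the power. With ±6 at one time point and no true difference, it is about 74% to 79% (90% interval) or 58% to 66% (95% interval) at 306 to 340 evaluable; a narrower margin lowers it.

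**Cost.** The preferred version changes one sentence and adds a short paragraph; test, sample size and data collection stay as they are. The price is that a claim of no effect becomes harder to make. With no true difference, 29% to 37% of trials would be inconclusive per unadjusted comparison, or 48% to 58% under the assumed Bonferroni adjustment. The general statement needs both time points to pass. Unadjusted, its chance with no true difference runs from 0.577² = 33% (306) or 0.659² = 43% (340) if the two estimates were independent, up to 58% or 66% if they were perfectly correlated. The documents give no such correlation.

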2.1 Purpose of the analyses

The analyses will assess recovery scores measured by QoR-15. The analyses will assess if there are differences in QoR-15 scores due to PCS intervention.

3 Study Objectives and Endpoints

3.1 Study Objectives

This study measures postoperative outcome of cancer patients undergoing SVP implantation evaluated with QoR-15 and the influence of PCS on postoperative recovery. The study was pre-planned within 'Patient-controlled sedation in subcutaneous port implantation- a randomized controlled trial' (PACSPI-2, EUDRACT NUMBER 2021-003821-31) which assesses the efficacy of patient-controlled sedation (PCS) with alfentanil and propofol as adjunct to local anaesthesia during SVP implantation. Patients participating in the study are interviewed with QoR-15 at three different time points; preoperatively (baseline), postoperative in PACU (before discharge) and 24 hours postoperatively (by telephone). Assessment of QoR-15 scores between groups and time points are the study objectives in these analyses.

3.2 Endpoints

Primary endpoint:

The primary endpoint is assessment of change in total QoR-15 score between groups at the time points.

Secondary endpoints:

Secondary endpoint is assessment of difference for each QoR dimension and for each of Parts A and B within and between groups.

Secondary endpoint is assessment of analgesic consumption and patient-reported postoperative pain perception between groups.

4 Study Methods

4.1 General Study Design and Plan

This is a pre-planned secondary study of the PACSPI-2 trial (NCT05688384).

In short:

The PACSPI-2 trial is an open multicentre randomized controlled trial with a study and a control arm in a 1:1 ratio. Patients are randomized to either a control arm of LA for SVP-implantation or a study arm of PCS with propofol and alfentanil as adjunct to LA for SVP-implantation. The aim is to randomize 340 patients with an estimated patient recruitment over 18 months. The trial is performed at two centres; Ryhov County Hospital, Jönköping, Sweden and Linköping University Hospital, Sweden. QoR-15 data is collected during the PACSPI-2 trial. Secondary outcomes include patient satisfaction, implantation conditions, sedation level, sedative and analgesic medication consumption, postoperative analgesic requirement, procedural time consumption as well as safety aspects and adverse events.

4.2 Inclusion-Exclusion Criteria and General Study Population

Inclusion criteria:

- Adult patients (≥ 18 years) with cancer scheduled for SVP-implantation at participating anesthesia departments.

Exclusion criteria:

- Inability to operate the PCS apparatus
- Inability to communicate in Scandinavian languages
- Patients who require general anesthesia or patients eligible for LA only on anesthesiologist's assessment (i.e. severe sleep apnea)
- Propofol or alfentanil allergy
- Non-fasting according to guidelines of the Swedish Society for Anesthesia and Intensive Care (SFAI)
- Failure to achieve peripheral vascular access
- Pregnancy
- Previous participation in study

4.3 Randomisation and Blinding

Prior to SVP-implantation and when the patient's eligibility has been confirmed and consent forms have been completed the patient is randomized by password-coded randomization software accessible to the co-investigators at each participating site (REDCap). All patients are randomized onto the study prior to SVP-implantation.

Each patient randomized will be allocated a unique sequential patient code number for the randomization arm together with an allocated study arm.

The randomization scheme is equal allocation (1:1). Randomization will be performed consecutively. If a patient withdraws from the trial the unique patient code will not be used again and the patient will not be included into the trial again.

4.4 Study Variables

All measured study variables are described in the PACSPI-2 study protocol accessible on clinicaltrials.gov (NCT05688384).

QoR-15swe (Quality of Recovery-15 Sweden) is measured on a numeric rating scale (NRS) from 0 to 10.

The score in the separate dimensions will be combined into a single value as expression for total QoR-15 score.

Del A

Hur har du mått de senaste 24 timmarna?

På en skala från 0 till 10, där 0 = Inte någon gång {dåligt} och 10 = hela tiden {utmärkt}

1	Kunnat andas lugnt	Inte någon gång	0	1	2	3	4	5	6	7	8	9	10	hela tiden
2	Kunnat njuta av maten	Inte någon gång	0	1	2	3	4	5	6	7	8	9	10	hela tiden
3	Känt dig utvildad	Inte någon gång	0	1	2	3	4	5	6	7	8	9	10	hela tiden
4	Kunnat sova gott	Inte någon gång	0	1	2	3	4	5	6	7	8	9	10	hela tiden
5	Kunnat sköta toalettbesök och personlig hygien utan hjälp	Inte någon gång	0	1	2	3	4	5	6	7	8	9	10	hela tiden
6	Kunnat kommunicera med anhöriga eller vänner	Inte någon gång	0	1	2	3	4	5	6	7	8	9	10	hela tiden
7	Fått stöd från sjukhuspersonal	Inte någon gång	0	1	2	3	4	5	6	7	8	9	10	hela tiden
8	Kan du utföra ditt arbete eller dina vanliga aktiviteter hemma	Inte någon gång	0	1	2	3	4	5	6	7	8	9	10	hela tiden
9	Känt dig trygg och haft kontroll över din tillvaro	Inte någon gång	0	1	2	3	4	5	6	7	8	9	10	hela tiden
10	Haft en känsla av allmänt välbefinnande	Inte någon gång	0	1	2	3	4	5	6	7	8	9	10	hela tiden

Del B

Har du känt något av följande symptom de senaste 24 timmarna?

på en skala från 10 till 0, där 10 = Inte någon gång {utmärkt} och 0 = hela tiden {dåligt}

11	Medelsvår smärta	Inte någon gång	10	9	8	7	6	5	4	3	2	1	0	hela tiden
12	Svår smärta	Inte någon gång	10	9	8	7	6	5	4	3	2	1	0	hela tiden

13	Illamående eller kräkning	Inte någon gång	10	9	8	7	6	5	4	3	2	1	0	hela tiden
14	Känt ångest eller oro	Inte någon gång	10	9	8	7	6	5	4	3	2	1	0	hela tiden
15	Känt dig ledsen eller deprimerad	Inte någon gång	10	9	8	7	6	5	4	3	2	1	0	hela tiden

Time table for measurement of variables

	Preop	Intraop	Postop	24h postop
QoR-15swe	x		x	x
Demographic	x			
Vital signs	x	x		
Procedure details		x		
Malignancy details	x			
Sedation assessment		x		
AE/SAE		x		
Analgesia		x		x
Time consumption	x	x	x	

5 Sample Size

Sample size calculation in the original trial was performed on its primary endpoint with the aim to detect a 50% reduction in pain perception as stated by the study protocol. 340 patients are included in the study with a 1:1 randomization.

Considering a minimal clinically important difference (MCID) of 6 that has been suggested to constitute a meaningful change in health status with a standard deviation of 19 a total number of 314 patients is needed to detect this change with 80% power, 2-sided, at a significance level of 5%.

6 General Considerations

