7.4 Follow-Up and End of Trial

Patients will be followed up until completion of QoR-15 day 1 after discharge. The end of trial will be defined as last patient last discharge.

8 Study Management

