10.1 Definition AE, SAE and SUSAR

AE: An adverse event (AE) is any untoward medical occurrence in a patient administered a pharmaceutical product and which does not necessarily have a causal relationship with this treatment. An AE can therefore be any unfavourable and unintended sign, symptom, or disease temporally associated with the use of a medicinal product, whether or not related to the medicinal product. All AE are documented on a separate form. Adverse events not separately documented are listed in Table 1.

Table 1

Symptom	Definition	Intervention
Respiratory depression	Bradypnea: breaths <8/min	verbal stimulation and advice to use PCS less frequent control patent airway chin lift/jaw thrust, establish patent airway oro-or naso-pharyngeal bag-valve mask ventilation
Desaturation	Saturation <90 %	Increase oxygen flow advice to use PCS less frequent check airway, proceed as under respiratory depression if needed
Compromised airway	1. patent 2. snoring 3. obstructed	If 2: advice patient to use PCS less frequent, chin lift. If 3 advice patient to use PCS less frequent, chin lift/jaw thrust;

		oro-or naso-pharyngeal airway; bag-valve mask ventilation Laryngeal mask or intubation
Bradycardia	Heart rate <40 / min	Atropin Efedrin
Hypotension	Hypotension (SBP <90mmHg) or difference >30% compared to baseline	Efedrin Fluid bolus Noradrenaline

SAE: A serious adverse event (SAE) is defined as any untoward medical occurrence that at any dose results in death, is life-threatening, requires inpatient hospitalization or causes prolongation of existing hospitalization, results in persistent or significant disability/incapacity, or requires intervention to prevent permanent impairment or damage. The investigator will follow all AE and SAE until judged to be clinically non-significant. Action taken and outcome of the AE/SAE are reported in the AE/SAE form.

All SAE are reported on a specific form to the sponsor within 24 hours.

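### AE/SAE collection is scheduled only during the procedure, so adverse events that first appear in PACU or by the 24-hour call depend on spontaneous reporting

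*Protocol*

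**What the plan says.** The Protocol is for the QoR-15 sub-study; the SAP is that of the parent PACSPI-2 trial.

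- **Protocol 4.4.** The table headed "Time table for measurement of variables" has four columns: preop, intraop, postop and 24h postop. AE/SAE has a single mark, under intraop. The same table marks QoR-15 at postop and 24 h, analgesia at 24 h, and time consumption at postop.
- **SAP 5.6.** Arterial puncture, pneumothorax and haematoma (variables 22-24) and hypoxia through nausea (variables 38-48) all have intra as registration time. The variables collected later are times, the patient questionnaire and QoR-15.
- **SAP 7.4.** "Patients will be followed up until completion of QoR-15 day 1 after discharge".
- **SAP 10.1.** An AE is an event "temporally associated with the use of a medicinal product, whether or not related to the medicinal product". "All AE are documented on a separate form"; the text then says that the events not documented separately are those in its Table 1 (respiratory depression, desaturation, compromised airway, bradycardia, hypotension). "All SAE are reported on a specific form to the sponsor within 24 hours". Once an event is found, "The investigator will follow all AE and SAE until judged to be clinically non-significant".
- **SAP 4.3.** Relative safety of the treatment arm belongs to the second objective.
- **Protocol 6.4 and SAP 6.6.1.** AEs are analysed after 100 and 200 patients against an expected frequency below 15%. No collection window is stated.

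**The concern.** The two contacts after theatre take place and collect data, but not on adverse events. A pneumothorax or haematoma that shows itself after theatre, or a respiratory or circulatory event in PACU, is not something that the schedule asks anyone to look for. The SAE definition includes an event that "requires inpatient hospitalization or causes prolongation of existing hospitalization". In a procedure usually done as day surgery, one would expect that criterion to be met after theatre, where the AE/SAE row is blank.

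What is at stake is the between-arm safety comparison. The trial is open (SAP 5.5.1), and only the study arm self-administers propofol and alfentanil. Where late events depend on someone choosing to mention them, the chance of a report may differ by arm. Neither the direction nor the amount of any such difference can be known from the documents.

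**Working it through.** The plan gives no rate of late events, so there is no figure of its own to reproduce. The sample sizes are not affected. The check is mainly a comparison of passages.

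**Step 1. What is scheduled at each contact**

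| Source | Procedure | PACU | 24 h call |
|---|---|---|---|
| Protocol 4.4, AE/SAE | marked | blank | blank |
| Protocol 4.4, QoR-15 | blank | marked | marked |
| Protocol 4.4, analgesia | marked | blank | marked |
| Protocol 4.4, time consumption | marked | marked | blank |
| SAP 5.6, variables 22-24 and 38-48 | intra | none | none |

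The blanks in the AE/SAE row are not explained by a lack of contact, and the parent trial's variable list shows the same pattern.

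**Step 2. Where an event first appearing after theatre would be recorded**

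- *Pneumothorax, haematoma, nausea.* These are not in SAP 10.1 Table 1, so the AE form applies if someone notices them. No question is planned that would bring them to notice as AEs.
- *Table 1 events.* These are exempt from the form. Their e-CRF fields are variable 39 (respiratory depression), 38 (desaturation), 40-41 (airway manoeuvres), 44 (bradycardia) and 46 (hypotension), all intra. One first occurring in PACU has neither form nor scheduled field unless it meets an SAE criterion.
- *SAEs.* The 24-hour reporting rule applies whenever the event becomes known. No enquiry is scheduled after theatre.
- *Follow-up.* SAP 10.1 and 10.2 on following events until they resolve concern events already found. They set no time at which new ones are sought.

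**Step 3. Whether the window could matter for the 15% check (illustration only)**

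Inputs from the documents: n = 100 and n = 200, threshold 15%. Assumptions: the frequency is the share of patients with at least one AE in both arms together; the intra-operative share is 8%, 10% or 12%; a further 0%, 2% or 5% of patients have only late events, all of which are counted.

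More than 15% means at least 16 of 100 or at least 31 of 200. With X binomial(n, p) and p the sum of the two shares, the chances P(X ≥ 16) at n = 100 and P(X ≥ 31) at n = 200 are:

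| Intra-operative | Late | n = 100 | n = 200 |
|---|---|---|---|
| 8% | 0% | 0.006 | 0.000 |
| 8% | 2% | 0.040 | 0.010 |
| 8% | 5% | 0.224 | 0.171 |
| 10% | 0% | 0.040 | 0.010 |
| 10% | 2% | 0.141 | 0.082 |
| 10% | 5% | 0.432 | 0.451 |
| 12% | 0% | 0.141 | 0.082 |
| 12% | 2% | 0.323 | 0.299 |
| 12% | 5% | 0.646 | 0.741 |

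Under these assumed rates the choice of window can decide whether the check is exceeded, so the window needs stating. The table is not evidence that late events occur at any of these rates.

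**The case against.** A reader might infer from the timetable that late complications go uncounted and that the reported AE rates are therefore too low. The SAP does not support that. Its AE definition rests on temporal association with the product, its form covers all AEs outside Table 1, and SAEs must reach the sponsor within 24 hours. None of this is limited to theatre, and SAP 7.1(g) lists procedural complications without a time limit. A late pneumothorax that comes to notice should be recorded. This part of the objection stands: under-ascertainment is a risk, not a certainty.

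Four further points have weight.

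- The timetable belongs to a sub-study with no AE endpoint, and Protocol 4.4 refers to a PACSPI-2 protocol that was not available here and might state a window. That limits certainty. It does not remove the point, because the parent trial's own SAP shows the same intra-operative pattern.
- Some intra codes are definitions. Variable 38 is hypoxia during the procedure, variable 39 is capnographic, and SAP 5.2 describes monitoring during the procedure only. Extending variables 38-47 to PACU would redefine them and would need further monitoring. This stands, and the fix leaves them alone.
- The 15% expectation comes from the feasibility trial, whose window the documents do not give. If it was intra-operative, a wider window would break the comparison. Exceeding 15% leads only to a discussion with the monitor, and SAP 6.6.2 sets no stopping rules. This argues for stating the window and reporting the periods separately.
- QoR-15 items 11-13 already ask about pain and about nausea or vomiting at both later contacts. They yield scores, however, not AE records.

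**Conclusion.** The point holds as a weakness in how safety events are sought. The schedule and the variable list are intra-operative only, SAP 10.1 is not, and no passage plans to look for new events in PACU or at the 24-hour call. The clearest gap is a non-serious Table 1 event that first occurs in PACU, which has no scheduled place to be recorded. Other late events rely on spontaneous reporting in an open trial.

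The size is unknown. The documents give neither a late-event rate nor a share of late events that would be missed, so no percentage of understatement can be defended. The conclusion rests on reading the Table 1 sentence in SAP 10.1 as an exemption from the form, and on the supplied documents being complete on this point. The QoR-15 analysis is unaffected. Because relative safety is a parent-trial objective and the remedy is cheap, the change should be made.

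**What to change.** 1. In Protocol 4.4, mark AE/SAE under postop and 24h postop, and state when the AE/SAE reporting period starts and ends.
2. Record AEs at PACU discharge, including any Table 1 event noted in routine care. Add one scripted AE/SAE question to the existing 24-hour call. Do both identically in the two arms.
3. In SAP 5.6, register pneumothorax, haematoma and nausea (variables 23, 24 and 48) at those contacts as well. Keep variables 38-47 intra-operative.
4. In SAP 10.1, say where a Table 1 event first seen after theatre is recorded, so that the text agrees with the timetable and the variable list.
5. Report intra-operative and post-operative AEs separately. In Protocol 6.4 and SAP 6.6.1, state which window the 15% check uses, so that it stays comparable with its benchmark.

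Cost: a few e-CRF fields, one extra question in a call already made, and an overall reported AE rate that may rise slightly. No added monitoring is implied, and the sample size does not change.
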